#### **7.3.8.3 Spondyloarthritis Research Consortium of Canada Enthesitis Index**

Assessment will be performed by the same assessor as the joint counts. The assessor will be trained by viewing the GRAPPA training module to perform the Spondyloarthritis Research Consortium of Canada (SPARCC) enthesitis assessment. The SPARCC enthesitis index assesses enthesitis at 18 sites with a resultant score of 0 to 16.

Tenderness at each site is assessed as 0 = non-tender or 1 = tender. Enteses assessed are left and right medial and lateral epicondyles, supraspinatus insertion into greater tuberosity of humerus, greater trochanter, quadriceps insertion into superior border of patella, patellar ligament insertion into inferior pole of patella, tibial tubercle, Achilles tendon insertion into calcaneum and bilateral plantar fascia insertion into the calcaneum. Higher count represents greater enthesitis burden. Tenderness at the inferior pole of patella and/or tibial tubercle will be scored as a maximum score of 1.

#### **7.3.8.4 Radiographs**

Radiographs of bilateral hands and feet will be taken in the required views: posterior/anterior for the hands and anterior/posterior for the feet. Radiographs will be done locally and read centrally.

The central imaging vendor will measure using the van der Heijde mTSS method for PsA. This method is based on the Sharp-van der Heijde method for assessing erosions and joint space narrowing of the hands and feet in RA and is adapted for evaluation of PsA by including the distal interphalangeal joints of the hand and scoring not only for erosions and joint space narrowing but also for subluxation, ankylosis, gross osteolysis, and pencil in cup phenomena. Erosions are scored from 0 to 3 in each joint and joint space narrowing is scored from 0 to 4 at each joint and includes assessment for ankylosis. Gross osteolysis and pencil in cup are scored separately. The maximum possible total score is 528. The radiographs will be read at a central location by two independent readers.

### **7.3.9 Psoriasis Disease Assessments**

#### **7.3.9.1 Static Physician Global Assessment of Psoriasis**

The assessor who conducts the tender and swollen joint counts will be trained and certified by GRAPPA training module to perform the Static Physician Global Assessment of Psoriasis (sPGA). The sPGA is designed to evaluate the physician's global assessment of the subject's psoriasis based on severity of induration, scaling, and erythema. The sPGA is assessed on a scale of 0 (clear) to 5 (severe).

#### **7.3.9.2 Body Surface Area Involvement**

The assessor who conducts the tender and swollen joint counts will be trained and certified by GRAPPA training module to perform the assessment for involved body surface area (BSA). BSA is a numerical score (0 to 100) used to measure the proportion of the subject's total BSA involvement with psoriasis.

#### **7.3.9.3 Modified Nail Psoriasis Severity Index**

The assessor who conducts the tender and swollen joint counts will be trained and certified by GRAPPA to perform the modified NAPSI assessment. The modified NAPSI scale is an objective, numeric, and reproducible grading system for nail psoriasis that incorporates the many different features of nail psoriasis. For assessments in this study (including selection of the target nail), a nail is graded on the following 8 clinical features and the modified NAPSI score results.

- pitting (scores 0-3, depending on the number of pits)
- nail plate crumbling (scores 0-3, depending on % of nail involvement)
- onycholysis and oil drop discoloration considered together (scores 0-3, depending on % of nail involvement)
- leukonychia (0 or 1 – absent or present)
- red spots in lunula (0 or 1 – absent or present)
- nail bed hyperkeratosis (0 or 1 – absent or present)
- splinter hemorrhages (0 or 1 – absent or present)

In randomized subjects with nails involved with psoriasis, each finger nail will be scored at baseline to determine the worst nail (ie, the nail with the highest modified NAPSI score); this nail will be followed for the remainder of the study. If multiple nails have the same worst score, only 1 target nail will be followed. Identify the selected nail in the source document and eCRF, if applicable.

#### **7.3.9.4 Physician Global Assessment of Disease Activity**

This assessment will be completed by either the joint assessor or the principal investigator (PI) for the study by completion of a visual analog scale (VAS). The VAS is 100 mm in length with “0” and “No Activity at All” on the left end of the line and “100” and “Worst Activity Imaginable” at the right end of the line. The subject and joint assessor or PI for the study must complete the global assessments independently from each other.

#### **7.3.10 Patient Reported Outcomes**

PRO assessments should be completed first (before other study procedures and administration of study medication) at each visit where they are required.

##### **7.3.10.1 Patient Global Assessment of Joint Pain**

The severity of the subject’s joint pain will be assessed by completion of a VAS. The horizontal line is 100 mm in length with “0” and “no pain at all” on the left end of the line and “100” and “worst pain imaginable” on the right end of the line. This questionnaire should take approximately 1 minute to complete.

##### **7.3.10.2 Patient Global Assessment of Disease Activity**

The subject’s global assessment of their arthritis disease activity will be assessed by completion of a VAS. The horizontal line is 100 mm in length with “0” and “No arthritis activity at all” on the left end of the line and “100” and “Worst arthritis activity imaginable” on the right end of the line. The subject and physician must complete the global assessments independently from each other. This questionnaire should take approximately 1 minute to complete.

##### **7.3.10.3 Disability Index of the Health Assessment Questionnaire**

The Disability Index of the Health Assessment Questionnaire (HAQ-DI) will be utilized to assess the subject’s physical function or disability according to the subject. The HAQ-DI asks about the degree of difficulty a person has in accomplishing tasks in 8 functional areas (dressing, arising, eating, walking, hygiene, reaching, gripping, and errands and chores). Responses in each functional area are scored from 0 indicating no difficulty to 3 indicating inability to perform a task in that area. The study staff should not clarify any of the questions for the subject. This questionnaire should take approximately 5 minutes to complete.

##### **7.3.10.4 Medical Outcomes Short Form-36 Questionnaire**

The Medical Outcomes Short Form-36 Questionnaire (SF-36) is a 36-item instrument that measures general health status. It includes 8 multi-item scales, each of which

assess 1 of the following 8 health concepts: 1) limitations in physical activities because of health problems; 2) limitations in social activities because of physical or emotional problems; 3) limitations in usual role activities because of physical health problems; 4) bodily pain; 5) general mental health (psychological distress and well-being); 6) limitations in usual role activities because of emotional problems; 7) vitality (energy and fatigue); and 8) general health perceptions. The SF-36 assesses the subject's perception of health status over the previous month and takes about 15 minutes to complete.

#### **7.4 Laboratory Assessments**

All screening and on-study laboratory samples will be processed and sent to the central laboratory with the exception of urine pregnancy, PPD, and Quantiferon (may be done by central or local laboratory). The central laboratory will be responsible for all screening and on-study serum chemistry, hematology, serum pregnancy, urinalysis, high sensitivity C-reactive protein, and any other laboratory tests required. Urine pregnancy and PPD testing, if applicable, will be performed locally with kits provided by the central laboratory (except PPD). The results of this testing will be maintained in the source documents at the site. Amgen or designee will be responsible for biomarker development and pharmacogenetic assessments, and the central laboratory will ship the samples to Amgen or a specialty laboratory for assay (depending on the assessment). The central laboratory will provide a study manual that outlines handling, labeling, and shipping procedures for all samples. All blood samples will be obtained by venipuncture before investigational product administration. The date and time of sample collection will be recorded in the source documents at the site. Specific analytes for serum chemistry, hematology, C-reactive protein, urinalysis, and other testing to be conducted on blood and urine samples are listed below ([Table 2](#)).

**Table 2. Analyte Listing**

Chemistry	Urinalysis	Hematology	Other Labs
Sodium	Specific gravity	WBC	Serum beta hCG a
Potassium	pH	Absolute neutrophil count	Hepatitis B surface antigen and Hepatitis B core antibody c
Chloride Bicarbonate	Blood	RBC	Hepatitis C virus antibody
Total protein	Protein	Hemoglobin	High sensitivity C-reactive protein
Albumin	Glucose	Hematocrit	Tuberculosis Testing b
Calcium	Bilirubin	MCV	
Adjusted calcium	Microscopic (Reflex testing if > trace)	MCH	
Magnesium		MCHC	
Phosphorus		RDW	
Glucose		Reticulocytes	
BUN or Urea		Platelets	
Creatinine		WBC Differential	
Uric acid		• Bands/stabs	
Total bilirubin		• Eosinophils	
Direct bilirubin		• Basophils	
Alkaline phosphatase		• Lymphocytes	
LDH		• Neutrophils	
AST (SGOT)		• Monocytes	
ALT (SGPT)			

a For all women, unless at least 2 years postmenopausal or history of hysterectomy, bilateral salpingectomy, or bilateral oophorectomy

b Subjects must receive either a PPD test or Quantiferon test at screening. National guidelines should be followed for appropriate tuberculosis screening in the setting of anti-TNF therapy.

c **At screening if the subject is positive for hepatitis B core antibody, the confirmatory reflex testing will be performed using HBV DNA PCR.**

#### 7.4.1 Tuberculosis Testing

National guidelines should be followed for appropriate tuberculosis screening in the setting of anti-TNF therapy.

All subjects must receive either a PPD or Quantiferon test at screening per

[Section 4.1.1](#).

##### 7.4.1.1 PPD

The PPD test must be read by a trained healthcare professional 48 to 72 hours after the test is placed.

##### 7.4.1.2 Quantiferon

If a subject does not receive a PPD test, then a Quantiferon test must be performed per [Section 4.1.1](#). Please refer to the central laboratory manual for instructions on sample collection, processing, and shipping of samples (if applicable).

#### **7.4.2 Urine Pregnancy Test**

Urine pregnancy tests will be performed locally at each site. The central laboratory will provide the urine pregnancy tests on visits where required. Urine pregnancy tests must be given prior to dispensing investigational product. If a urine pregnancy test is positive, investigational product must be held; if pregnancy is confirmed, then investigational product must be discontinued.

#### **7.5 Biomarker Development**

Biomarkers are objectively measured and evaluated indicators of normal biologic processes, pathogenic processes, or pharmacologic responses to a therapeutic intervention. Biomarker development can be useful in developing markers to identify disease subtypes, guide therapy, and/or predict disease severity.

Amgen may attempt to develop test(s) designed to identify subjects most likely to respond positively or negatively to etanercept and/or methotrexate. Biomarker development may be pursued by use of advanced biochemical analyses, such as proteomic methods or ribonucleic acid transcript profiling. A cell pellet from the blood plasma tube may be utilized to assess the impact of etanercept and/or methotrexate on circulating immune cells via deoxyribonucleic acid (DNA) methylation analysis, a pharmacodynamic assessment of methylation patterns of relevant genes. The DNA extracted will not be used for optional pharmacogenetic analyses unless the subject signs the additional consent.

#### **7.6 Pharmacogenetic Studies**

If the subject consents to the optional pharmacogenetic portion of this study, DNA analyses may be performed. These optional pharmacogenetic analyses focus on inherited genetic variations to evaluate their possible correlation to the disease and/or responsiveness to the therapies used in this study. The goals of the optional studies include the use of genetic markers to help in the investigation of PsA and/or to identify subjects who may have positive or negative response to Amgen and non-Amgen investigational product. No additional samples are collected for this part of the study. For subjects who consent to this/these analysis/analyses, DNA may be extracted.

#### **7.7 Sample Storage and Destruction**

Any blood sample collected according to the Schedule of Assessments ([Table 1](#)) can be analyzed for any of the tests outlined in the protocol and for any tests necessary to minimize risks to study subjects. This includes testing to ensure analytical methods produce reliable and valid data throughout the course of the study. This can also

include, but is not limited to, investigation of unexpected results, incurred sample reanalysis, and analyses for method transfer and comparability.

All samples and associated results will be coded prior to being shipped from the site for analysis or storage. Samples will be tracked using a unique identifier that is assigned to the samples for the study. Results are stored in a secure database to ensure confidentiality.

If informed consent is provided by the subject, Amgen can do additional testing on remaining samples (ie, residual and back-up) to investigate and better understand inflammatory conditions, the dose response and/or prediction of response to etanercept or methotrexate, and characterize aspects of the molecule (eg, mechanism of action/target, metabolites). Results from this analysis are to be documented and maintained, but are not necessarily reported as part of this study. Samples can be retained for up to 20 years.

Since the evaluations are not expected to benefit the subject directly or to alter the treatment course, the results of pharmacogenetic, biomarker development, or other exploratory studies are not placed in the subject's medical record and are not to be made available to the subject, members of the family, the personal physician, or other third parties, except as specified in the informed consent.

The subject retains the right to request that the sample material be destroyed by contacting the investigator. Following the request from the subject, the investigator is to provide the sponsor with the required study and subject number so that any remaining blood samples and any other components from the cells can be located and destroyed. Samples will be destroyed once all protocol-defined procedures are completed. However, information collected from samples prior to the request for destruction, will be retained by Amgen.

The sponsor is the exclusive owner of any data, discoveries, or derivative materials from the sample materials and is responsible for the destruction of the sample(s) at the request of the subject through the investigator, at the end of the storage period, or as appropriate (eg, the scientific rationale for experimentation with a certain sample type no longer justifies keeping the sample). If a commercial product is developed from this research project, the sponsor owns the commercial product. The subject has no commercial rights to such product and has no commercial rights to the data, information,

discoveries, or derivative materials gained or produced from the sample. See [Section 11.3](#) for subject confidentiality.

## **8. WITHDRAWAL FROM TREATMENT, PROCEDURES, AND STUDY**

### **8.1 Subjects' Decision to Withdraw**

Subjects have the right to withdraw from the study at any time and for any reason without prejudice to their future medical care by the physician or at the institution.

Subjects can decline to continue receiving investigational product and/or other protocol-required therapies or procedures at any time during the study but continue participation in the study. If this occurs, the investigator is to discuss with the subject the appropriate processes for discontinuation from investigational product or other protocol-required therapies and must discuss with the subject the options for continuation of the Schedule of Assessments ([Table 1](#)) and collection of data, including endpoints and adverse events. The investigator must document the change to the Schedule of Assessments ([Table 1](#)) and the level of follow-up that is agreed to by the subject (eg, in person, by telephone/mail, through family/friends, in correspondence/communication with other physicians, from review of the medical records).

Withdrawal of consent for a study means that the subject does not wish to receive further protocol-required therapies or procedures, and the subject does not wish to or is unable to continue further study participation. Subject data up to withdrawal of consent will be included in the analysis of the study, and where permitted, publically available data can be included after withdrawal of consent. The investigator is to discuss with the subject appropriate procedures for withdrawal from the study. The data generated may potentially not be included in the subject's study data, except in the case of a possibly related serious adverse event, where data will be collected.

### **8.2 Investigator or Sponsor Decision to Withdraw or Terminate Subjects' Participation Prior to Study Completion**

The investigator and/or sponsor can decide to withdraw a subject(s) from investigational product and/or other protocol-required therapies, protocol procedures, or the study as a whole at any time prior to study completion.

Subjects may be eligible for continued treatment with Amgen investigational product(s) and/or other protocol-required therapies by a separate protocol or as provided for by the local country's regulatory mechanism, based on parameters consistent with [Section 12.1](#).

---

### **8.3 Reasons for Removal From Treatment or Study**

#### **8.3.1 Reasons for Removal From Treatment**

Reasons for removal from protocol-required investigational product(s) or procedural assessments include any of the following:

- subject request
- safety concern (eg, due to an adverse event, ineligibility determined, protocol deviation, non-compliance, requirement for alternative therapy, pregnancy)
- death
- lost to follow-up
- decision by sponsor (other than subject request, safety concern, death or lost to follow-up)
- disease flare requiring treatment not allowed in the protocol (eg, colitis, asthma)

#### **8.3.2 Reasons for Removal From Study**

Reasons for removal of a subject from the study are:

- decision by sponsor
- withdrawal of consent from study
- death
- lost to follow-up

## **9. SAFETY DATA COLLECTION, RECORDING, AND REPORTING**

### **9.1 Adverse Events**

#### **9.1.1 Definition of Adverse Events**

An adverse event is defined as any untoward medical occurrence in a clinical trial subject. The event does not necessarily have a causal relationship with study treatment. The investigator is responsible for ensuring that any adverse events observed by the investigator or reported by the subject are recorded in the subject's medical record.

The definition of adverse events includes worsening of a pre-existing medical condition. Worsening indicates that the pre-existing medical condition (eg, diabetes, migraine headaches, gout) has increased in severity, frequency, and/or duration, and/or has an association with a significantly worse outcome. A pre-existing condition that has not worsened during the study or involves an intervention such as elective cosmetic surgery or a medical procedure while on-study, is not considered an adverse event.

The investigator's clinical judgment is used to determine whether a subject is to be removed from treatment due to an adverse event. In the event a subject, or subject's legally acceptable representative requests to withdraw from protocol-required therapies

or the study due to an adverse event, refer to [Section 8.1](#) for additional instructions on the procedures recommended for safe withdrawal from protocol-required therapies or the study.

### **9.1.2 Definition of Serious Adverse Events**

A serious adverse event is defined as an adverse event that meets at least 1 of the following serious criteria:

- fatal
- life threatening (places the subject at immediate risk of death)
- requires in-patient hospitalization or prolongation of existing hospitalization
- results in persistent or significant disability/incapacity
- congenital anomaly/birth defect
- other medically important serious event

An adverse event would meet the criterion of “requires hospitalization”, if the event necessitated an admission to a health care facility (eg, overnight stay).

If an investigator considers an event to be clinically important, but it does not meet any of the serious criteria, the event could be classified as a serious adverse event under the criterion of “other medically important serious event”. Examples of such events could include allergic bronchospasm, convulsions, blood dyscrasias, DILI (see [Appendix A](#) for DILI reporting criteria), or events that necessitate an emergency room visit, outpatient surgery, or urgent intervention.

## **9.2 Reporting of Adverse Events**

### **9.2.1 Reporting Procedures for Adverse Events That do not Meet Serious Criteria**

The investigator is responsible for ensuring that all adverse events observed by the investigator or reported by the subject that occur after first dose of investigational product(s) through the end of treatment period are reported using the applicable CRF (eg, Adverse Event Summary).

The investigator must assign the following adverse event attributes:

- Adverse event diagnosis or syndrome(s), if known (if not known, signs or symptoms),
- Dates of onset and resolution (if resolved),
- Severity (and/or toxicity per protocol),
- Assessment of relatedness to investigational product(s) and
- Action taken.

The adverse event grading scale used will be the Common Toxicity Criteria Version 4. The grading scale used in this study is described in [Appendix A](#). The investigator must assess whether the adverse event is possibly related to the investigational product(s). This relationship is indicated by a “yes” or “no” response to the question: Is there a reasonable possibility that the event may have been caused by the investigational product(s)?

The investigator is responsible for reviewing laboratory test results and determining whether an abnormal value in an individual study subject represents a clinically significant change from the subject’s baseline values. In general, abnormal laboratory findings without clinical significance (based on the investigator’s judgment) are not to be recorded as adverse events. However, laboratory value changes that require treatment or adjustment in current therapy are considered adverse events. Where applicable, clinical sequelae (not the laboratory abnormality) are to be recorded as the adverse event.

The Investigator is expected to follow reported adverse events until stabilization or reversibility.

If the severity of an adverse event changes from the date of onset to the date of resolution, record as a single event with the worst severity on the Adverse Event Summary CRF.

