**Table 1. Schedule of Assessments**

Weeks	30-day Screening	Treatment Period								Disease Assessment (DA)		30-day Follow-Up Safety (EOS) g
		0 (day 1)	4	8	12	16	24	36	48/ET	DA Visit e	DA Follow-up e	
PATIENT REPORTED OUTCOMES												
Patient global assessment of pain (VAS 0 to 100)		X	X	X	X	X	X	X	X	X	X	X
Patient global assessment of disease activity (VAS 0 to 100)		X	X	X	X	X	X	X	X	X	X	X
Disability Index of the Health Assessment Questionnaire (HAQ-DI)		X	X	X	X	X	X	X	X	X	X	X
Medical Outcomes Short Form-36 Questionnaire (SF-36)		X			X		X	X	X			

Page 2 of 2

ET: early termination; DA: Disease Assessment; EOS: end of study; **HBV: hepatitis B virus**; IXRS: Interactive voice response system; **PCR: polymerase chain reaction**; VAS: visual analog scale

aScreening physical exam will be a full exam; subsequent exams per standard of care to monitor for any changes

bFor all women, unless at least 2 years postmenopausal or history of hysterectomy, bilateral salpingectomy, or bilateral oophorectomy

cAdditional pregnancy testing may be completed at the discretion of the investigator

dSubjects will receive either a PPD test or Quantiferon test at screening. National guidelines should be followed for appropriate tuberculosis screening in the setting of anti-TNF therapy.

eDisease Assessment Visit - disease activity may be assessed at a regularly scheduled visit or at a Disease Assessment visit as described in [Section 7.2.5](#). If subject initiates rescue treatment then they must return for a Disease Assessment Follow-up visit 4 to 5 weeks later.

fIf subjects meet the criteria for inadequate response as described in [Section 3.1.2](#) they will be allowed to receive rescue treatment with etanercept plus methotrexate

gSubjects will be contacted by phone by the site staff to collect any serious adverse events

hFrequency of dispensation will vary with quantity dispensed and individual subject dose

i **At screening if the subject is positive for hepatitis B core antibody, the confirmatory reflex testing will be performed using HBV DNA PCR.**

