#### **7.2.7 Safety Follow-up/End of Study**

Approximately 30 days, within a window of + 7 days of the target visit date, after the last dose of investigational products, subjects will be contacted by phone by the site staff to collect any serious adverse events (refer to [Section 9](#)).

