### **9.2.2 Reporting Procedures for Serious Adverse Events**

The investigator is responsible for ensuring that all serious adverse events observed by the investigator or reported by the subject that occur after signing of the informed consent through 30 days after the last day of the dosing interval of investigational product(s) are recorded in the subject’s medical record and are submitted to Amgen. All serious adverse events must be submitted to Amgen within 24 hours following the investigator’s knowledge of the event via the applicable eCRF.

After the protocol-required reporting period defined above, the investigator does not need to actively monitor subjects for serious adverse events. However, if the investigator becomes aware of a serious adverse event after this protocol-required reporting period, the investigator will report the event to Amgen within 24 hours following the investigator’s knowledge of the event. Serious adverse events reported outside of the protocol-required reporting period will be captured within the safety database as clinical trial cases for the purposes of expedited reporting.

If the electronic data capture (EDC) system is unavailable to the site staff to report the serious adverse event, the information is to be reported to Amgen via an eSAE Contingency Report Form within 24 hours of the investigator's knowledge of the event. See [Appendix B](#) for a sample of the Serious Adverse Event Worksheet/eSAE Contingency Report Form. For EDC studies where the first notification of a Serious Adverse Event is reported to Amgen via the eSAE Contingency Report Form, the data must be entered into the EDC system when the system is again available.

The investigator must assess whether the serious adverse event is possibly related to any study-mandated activity or procedure. This relationship is indicated by a "yes" or "no" response to the question: "Is there a reasonable possibility that the event may have been caused by a study activity/procedure?"

The investigator is expected to follow reported serious adverse events until stabilization or reversibility.

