6.3 Study Dates

End of Study Date

Date of the End of Study (EOS) safety follow-up phone call (for subjects who complete the study) or Early Termination (ET) visit (for subjects who withdraw from the study prematurely).

First Dose Date

The date of the first dose of IP.

Last Dose Date

The date of the last dose of IP.

Randomization Date

The date when a randomization number is assigned through the Interactive Voice/Web Response System (IVRS/IWRS).

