lateral epicondyle (left and right), supraspinatus insertion into greater tuberosity of humerus (left and right), greater trochanter (left and right), quadriceps insertion into superior border of patella (left and right), patellar ligament insertion into inferior pole of patella or tibial tubercle (left and right), Achilles tendon insertion into calcaneum (left and right), plantar fascia insertion into calcaneum (left and right). A higher count represents greater enthesitis burden.

Details of the scoring algorithm are described in [Appendix A](#).

Static Physician Global Assessment of Psoriasis (sPGA)

The static Physician Global Assessment of psoriasis (sPGA) evaluates the physician's global assessment of the subject's psoriasis based on severity of induration, scaling, and erythema. The sPGA is assessed on a scale of 0 (clear) to 5 (severe).

Swollen Joint Count

A score that assesses the presence or absence of swelling in 66 joints. Details of the scoring algorithm are described in [Appendix A](#).

Tender Joint Count

A score that assesses the presence or absence of tenderness in 68 joints. Details of the scoring algorithm are described in [Appendix A](#).

Treatment Emergent AE

A treatment emergent AE is defined as an event that occurs on or after the initiation of the IP and prior to the EOS date (ie, 30 days after last dose of IP). It is determined by the pre-treatment flag (ie, AE.AEPRETRT NE 'Y') on the Events CRF with a start date up to 30 days after the end of investigational product or the End of Study date, whichever is earlier.

Van der Heijde Modified Total Sharp Score (mTSS)

A method for assessing erosions and joint space narrowing of the hands and feet based on the Sharp-van der Heijde method in rheumatoid arthritis. The method is adapted for evaluation of PsA by including the distal interphalangeal joints of the hand and scoring not only for erosions and joint space narrowing but also for subluxation, ankylosis, gross osteolysis, and pencil in cup phenomena. The maximum possible total score is 528.

A higher score represents worse destruction. Details of the scoring algorithm are described in [Appendix A](#).

Very Low Disease Activity (VLDA)

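### The SAP's treatment-emergent window runs past the end of non-serious event collection, and the follow-up call can come before the serious-event period closes

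*Protocol*

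**What the plan says.** **Non-serious events.** Protocol 9.2.1 requires reporting of events "that occur after first dose of investigational product(s) through the end of treatment period are reported using the applicable CRF". Table 1 agrees: the adverse events row has no mark in the 30-day follow-up column, and the serious adverse events row does.

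**The follow-up contact.** Protocol 7.2.7 times it at "Approximately 30 days, within a window of + 7 days of the target visit date, after the last dose of investigational products", and its content is that "subjects will be contacted by phone by the site staff to collect any serious adverse events". A footnote to Table 1 says the same.

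**Serious events.** Protocol 9.2.2 runs collection from consent "through 30 days after the last day of the dosing interval of investigational product(s)". After that period the investigator need not monitor actively, but must still report any serious event that becomes known.

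**What the SAP counts.** SAP 6.6 (Treatment Emergent AE) first ends the window "prior to the EOS date (ie, 30 days after last dose of IP)". It then gives the working rule: an event "with a start date up to 30 days after the end of investigational product or the End of Study date, whichever is earlier".

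**End of Study date.** SAP 6.3 defines it as "Date of the End of Study (EOS) safety follow-up phone call (for subjects who complete the study) or Early Termination (ET) visit", the latter for subjects who withdraw prematurely.

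**The concern.** Three places in the Protocol (9.2.1, Table 1, 7.2.7) agree that only serious events are sought after treatment ends. The SAP window extends about a month past the end of product for all events. SAP section 11, which lists departures from the protocol analyses, does not mention the difference.

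Treatment-emergent incidence is the central safety output in SAP 10.6.1. A reader who sees the 30-day definition will assume that non-serious events were looked for over those 30 days. For completers, most of that time has no planned collection.

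Two smaller mismatches sit next to it. The serious-event period is counted from the end of the dosing interval and the call from the last dose, so the only scheduled contact can come before the period it serves has closed. And SAP 6.6 equates the End of Study date with 30 days after last dose, while SAP 6.3 gives a different date for early withdrawals.

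**Working it through.** **Inputs**
- One dose per week for 48 weeks, about 7 days apart (Protocol 6.2.1.1, 6.2.2.1).
- First dose on day 1 (Protocol 7.2.3).
- End of treatment visit at week 48, ±7 days (Protocol 7.2.6); target study day 337 (SAP Appendix A).
- Follow-up call 30 days after last dose, +7 days (Protocol 7.2.7).
- Serious-event period: end of dosing interval + 30 days (Protocol 9.2.2).
- Assumption: no missed or late doses.

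**The plan's own figure.** Protocol 3.5.1 gives participation of about 56 weeks. (30 + 336 + 30)/7 = 56.6 weeks, so the stated duration is reproduced.

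**Step 1: non-serious gap for a completer**
- Last scheduled dose: 1 + 47 × 7 = day 330.
- SAP window closes: 330 + 30 = day 360.
- Non-serious collection stops at the week 48 visit.

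| Week 48 visit | Days of SAP window with no planned non-serious collection | Share of 360 days |
|---|---|---|
| Day 330 (−7) | 360 − 330 = 30 | 8.3% |
| Day 337 (target) | 360 − 337 = 23 | 6.4% |
| Day 344 (+7) | 360 − 344 = 16 | 4.4% |

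If the last dose were instead taken on the day of the visit (day 337), the gap would be 367 − 337 = 30 days.

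**Step 2: serious-event period against the call**
- Period closes 7 + 30 = 37 days after last dose, or 6 + 30 = 36 days if the dose day counts as the first day of the interval.
- The call may fall on days 30 to 37 after last dose.
- Call on the day-30 target: 37 − 30 = 7 days, or 36 − 30 = 6 days, of the required period come after the contact.
- The whole period is covered only by a call on day 37, or on days 36 to 37 under the narrower count.
- Serious events starting on days 31 to 37 (or 31 to 36) are inside the Protocol period but outside the SAP's 30-day cap.

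**Step 3: early withdrawals**
- Under SAP 6.3 the End of Study date is the early termination visit. If that visit is k days after last dose, with k below 30, the SAP window closes at day k because the earlier date applies.
- The Protocol serious-event period still runs to day 36 or 37, so 37 − k days (36 − k on the narrower count) lie inside the Protocol period and outside the treatment-emergent definition. For k = 7 that is 30 (29) days.
- Protocol 7.2.7 does not restrict the call to completers. A serious event collected at the call from an early withdrawal could therefore be excluded by definition.
- The non-serious gap largely disappears for these subjects, because window and collection both end at about the same visit.

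**The case against.** **Ending non-serious collection at end of treatment is a legitimate choice, stated consistently.** That stands. The Protocol is coherent on this; the conflict is with the SAP window. One can also say that the SAP definition only filters events already collected, and that its 30-day tail serves to let late serious events count. The SAP does not say so, and it plans simple subject incidence with no exposure-adjusted rate, so the uncollected days distort no planned denominator. The effect is limited to what the table claims to cover.

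**A reader might infer that all of the last 30 days are empty.** Under the planned schedule the week 48 visit falls about 7 days after the last dose, so the usual gap is 23 days. Thirty is the extreme.

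**A reader might infer differential ascertainment between arms.** Protocol 8.1 lets a subject stop product and stay on the visit schedule, and such a subject can have non-serious events collected throughout the 30 days. If early stops differed by arm, completeness of the window could differ too. The documents do not support going further. The collection rule is identical in every arm, no discontinuation rates by arm are given, and the level of follow-up after stopping is agreed subject by subject. An early stopper also fills a larger share of a much shorter window and does not have more collection in total.

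**A reader might infer that late serious events are lost.** They are not exempt from reporting. Protocol 9.2.2 keeps the investigator responsible to the end of the period, and events learned of later must still be sent within 24 hours. A call made late in its window covers the whole period. The shortfall is in scheduled contact only.

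**Conclusion.** The mismatch is real and small. For a completer on schedule, about 23 of 360 days (6.4%; range 16 to 30 days, 4.4% to 8.3%) of the SAP's treatment-emergent window have no planned non-serious collection, so the table under-collects against its own definition. A follow-up call on its target date leaves 6 to 7 days of the required serious-event period without scheduled contact. SAP 6.3 and 6.6 disagree on the End of Study date for early withdrawals, which puts some serious events that the Protocol requires outside the treatment-emergent definition.

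The day counts assume dosing from day 1 with no missed doses. The choice between 6 and 7 days depends on how the dosing interval is counted, which the Protocol does not state. No between-arm bias is shown, and no efficacy, alpha or sample-size figure is affected. This is a low-cost improvement to safety ascertainment and wording.

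**What to change.** 1. At the existing follow-up call, ask about all adverse events, serious and non-serious, since the last visit. Mark the adverse events row in the follow-up column of Table 1, and amend Protocol 7.2.7 and 9.2.1 to match.
2. Schedule the call on or after the last day of the serious-event period. On present wording that is no earlier than 37 days after last dose (36 on the narrower count). State how the dosing interval is counted.
3. Use one anchor and one end date in Table 1, Protocol 7.2.7, 9.2.1 and 9.2.2, and SAP 6.3 and 6.6, so that early withdrawals are not cut off at the early termination visit. Remove the gloss in SAP 6.6 that equates the End of Study date with 30 days after last dose, or make it true.

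If collection is not changed, end the SAP's treatment-emergent window for non-serious events at end of treatment, say so in the table, and still reconcile SAP 6.3 with 6.6.

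**Cost.** A few more adverse event entries from a call that is already made, and a call up to 7 days later than its current target. No visit is added. With the last dose on day 330 and the call 37 days later, participation is (30 + 329 + 37)/7 = 56.6 weeks, still in line with the stated duration of about 56 weeks.
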